[name],
Argentina –[contact] - [contact].

Ethics Committee Participant:

Research Ethics Committee at DIM Clínica

Privada

[name]
Buenos Aires Argentina, [contact]

Version History

Number of substantial amendment	Final version involved	Nature of the amendment
1	17Aug2021	Request for changes by the Regulatory Authority –Communication #01
		
Dose selection is accounted for
 
Changes were made to the window periods for COVID19 vaccines for the first and second doses
 
The possibility of voluntarily withdrawing from the study is made explicit to the volunteer given the immediate possibility of receiving COVID19 vaccine
 
The number of volunteers to be hospitalized is clarified

2	02Sept2021	Response to stopclock by ANMAT dated 13 September, 2021
		
Rationale was extended to justify the dose
 
The possibility of receiving a COVID vaccine was added as a criterion for withdrawal from the study
 
The number of volunteers to be admitted was changed
 
The window of time in which the volunteer may receive COVID-19 vaccine was clarified in an inclusion criterion

Amendment Version 1 – 17Aug2021

Reviews for version dated July 20, 2021 are the following:

Justification for dose selection:

Section # 7 DOSING REGIMEN AND ADMINISTRATION, the following statement was added to account for the selected dose:

“A dose of 1mg/kg is the one that did not cause adverse events in preclinical animal studies, conducted with the same Biosidus molecule, which defines this dose as the NOAEL (Non observed adverse event level).”

Changes in the exclusion criteria:

New Exclusion Criterion #7 (*Exclusion Criterion #7: Reception of live or dead virus, bacteria vaccines, including COVID-19 vaccine (In this case, patients who have received a single dose of vaccine in the month prior to recruitment will be excluded.)*)

It was divided into two parts to clearly state the window periods for the COVID-19 vaccine):

Exclusion Criterion #7: Reception of live or dead virus, bacteria vaccines within fifteen days prior to visit 1 or 2.

The following Exclusion Criterion is added:

Exclusion Criterion #8: In the case of COVID vaccines, a window period longer than 15 days must be observed before visits 1 or 2. This period is contemplated based on the recommendations by the National Ministry of Health published on 5-29-2021.

Possibility of withdrawing from the study due to the potential for receiving COVID-19 vaccine:

In the section STUDY COURSE AND PROCEDURES the following statement was added related to COVID-19 Vaccine:

"Note: The participant may withdraw from the study at any time if they decide to receive the first or second dose of the COVID vaccine during the study."

Number of volunteers to be hospitalized:

The following clarification regarding the number of volunteers to be hospitalized was added to the item VISIT II (Hospitalization):

"The rest of the volunteers will be hospitalized in three groups of 6 volunteers (in compliance with the number of volunteers for bioequivalence studies according to authorizing provision, see Annex F) as described in the section Study course and Procedure - Visit II (Hospitalization)."

Amendment Version 2 – 02Sept2021

Revisions for Amendment 1 dated August 17, 2021 are the following:

Dose justification:

The rationale was extended to justify the recommended dose of 1 mg/kg /body weight of agalsidase beta.

Withdrawal from the study due to COVID vaccine:

The following text was removed: "Note: the participant may withdraw from the study at any time if they decide to receive the first or second dose of the COVID vaccine during the study". The text was modified and included as a criterion for study withdrawal: "Participant who has the possibility of receiving the first or second dose of the COVID vaccine during the study"

Number of patients to be hospitalized:

In relation to the site authorization for the development of phase 1 clinical trials and bioequivalence by Provision No. 5344/2019, as it is a phase I trial, the use of up to 2 simultaneous beds is authorized. For this reason, the hospitalization of the volunteers was adapted as authorized and a staggered hospitalization will be carried out (see Visit II (Hospitalization)).

Clarification for exclusion criterion:

The following text was added to exclusion criterion #8: "Volunteer may receive the vaccine 35 days after receiving the investigational product." to make clear the time window in which the volunteer may receive the COVID-19 vaccine.

PROTOCOL SUMMARY

TITLE	COMPARATIVE STUDY ON THE PHARMACOKINETICS AND PHARMACODYNAMICS BETWEEN TWO AGALSIDASE BETA FORMULATIONS IN A SINGLE DOSE OF 1 MG/KG AGALSIDASE (BIOSIDUS) AND FABRAZYME® (SANOFI GENZYME) BY INTRAVENOUS INFUSION IN HEALTHY MALE VOLUNTEERS
CODE	RD-BIO-AGA-01/03/21
SPONSOR	Biosidus S.A. [name] [contact] [contact]
PRINCIPAL INVESTIGATOR	[name] [name] [contact]
CO – INVESTIGATOR	[name]
REGULATORY HEAD	[name]
SITE	Sanatorio Nuestra Señora del Pilar [name]
LABORATORIES	
 • Enzyme Activity Assessment: Biosidus Development Department - [name], Argentina - [contact] - [contact] • Immunogenicity Assessment: Biosidus Development Department - [name], Argentina - [contact] - [contact] • Pharmacokinetic Assessment: Shin Nippon Biomedical Laboratories, Ltd., [name], [contact]; [contact]
PRIMARY OBJECTIVE	Compare the pharmacokinetic behavior of Biosidus Agalsidase beta and Fabrazyme® (Genzyme) after administration by intravenous infusion of 1 mg/kg over a period of 5 hours of one of the following formulations: - Fabrazyme®, by Sanofi Genzyme (Reference Formulation, "R") - Agalsidase beta, biosimilar developed by Biosidus SA (Test Formulation, "T")

SECONDARY OBJECTIVE	Evaluation of enzyme activity, product safety, incidence of adverse events and tolerance. Evaluation of antibody occurrence.
STUDY DESIGN	Open, randomized, parallel-arms, balanced, single-dose, and sequential
DISCONTINUATION SCHEDULE	The sponsor and investigators may independently discontinue the study at any time at the sole possibility or occurrence of a serious adverse event or situation that could affect the volunteer's health.
NUMBER OF VOLUNTEERS	A total of 20 (twenty) male volunteers will initially be included. As it is a sequential design, if the statistical analysis on the first 20 volunteers does not demonstrate bioequivalence, an additional number of healthy volunteers to be determined will be included to verify the similarity criterion with adequate power.
SCREENING CRITERIA	
INCLUSION CRITERIA:
 
 1) Male subjects aged between 18 and 40 years. 2) Body mass index (BMI) between 19 and 25 kg/m². 3) Volunteers whose investigations (ECG, chest X-ray, blood and urine, PCR for COVID-19), performed prior to their inclusion and are within normal limits and/or without clinical significance at the investigator's discretion. 4) Subjects with systolic blood pressure higher than 110 mm Hg and lower than 139 mm Hg, a diastolic pressure higher than 70 mm Hg and lower than 89 mm Hg with a heart rate higher than 50 and lower than 90 beats per minute after being 5 minutes in a sitting position and then in a standing position (outliers included). 5) Volunteer being willing to participate in the study and who has signed the informed consent approved before the study initiation. 
EXCLUSION CRITERIA:
 
 1) History of clinically significant allergies (except asymptomatic untreated seasonal allergies). 2) ≥ 20 mm Hg drop in systolic pressure or ≥ 10 mm Hg in diastolic pressure in the first 3 minutes of postural change. 3) Volunteers who are or have been taking other drugs (prescription or over-the-counter) within two weeks prior to the study. 4) Volunteers with a history of autoimmune diseases. 5) Organic CNS mental and/or psychiatric conditions: bipolar disorder, severe depression, insomnia, changes in personality. 6) Active or chronic infections

7) Reception of live or dead virus, bacteria vaccines within fifteen days prior to visit 1 or 2.

8) In the case of COVID vaccines, a window period longer than 15 days must be observed before visits 1 or 2. This period is contemplated based on the recommendations by the National Ministry of Health published on 5-29-2021. The volunteer may receive the vaccine 35 days after receiving the investigational product.

9) Known allergy to any of the components of the formulations.

10) Active smoker of more than 10 cigarettes/day.

11) Current clinical evidence of severe digestive disorders, digestive tract surgeries (except appendectomy)

12) Current clinical evidence of kidney disease.

13) Current evidence of liver disorders

14) Current clinical evidence of respiratory and cardiac diseases.

15) Presence of diabetes mellitus, thyroid dysfunction or other endocrine disorder.

16) Evidence of active gastroduodenal disease.

17) History of peripheral thrombotic phenomena.

18) Underlying neurological disease

19) Current presence of any progressive chronic disease

20) History of drug or alcohol abuse or addiction during the last three years.

21) Participation in a clinical study within the last three months.

22) Use of any drug within fourteen days prior to the study initiation that, at the principal investigator's discretion, may interfere with the drug biodistribution.

23) Subject who donated or experienced blood loss within the last twelve weeks prior to the study initiation, or willing to donate blood within three months after the end of the study.

24) Excessive drinker of tea, cocoa, mate, coffee and/or beverages containing caffeine (>5 cups/day) or wine (>0.5 L/day) or alcoholic drinks (>50 ml/day).

25) Significant abnormalities in the electrocardiogram

26) PCR positive for COVID-19.

	
27) Serology positive for HIV, hepatitis B or hepatitis C.
 
28) Abnormal clinical laboratory results (which, at the principal investigator's discretion, are considered clinically significant)
 
29) Non-cooperative volunteer

STUDY DURATION PER VOLUNTEER	Duration of the clinical study 56 days per volunteer: 21 days (screening) and 35 days (follow-up until end-of-study visit)
STUDY VISITS	
 • Visit I: Selection of volunteers, obtaining informed consent and completion of entrance exams. • Visit II: It will consist of a 24-h hospitalization for the administration of the R or T product, assigned according to the volunteer randomization. Sampling times for the investigational product pharmacokinetic quantification for each volunteer will be: pre-dose (0 h), 1 h, 3 h, 5 h, 5.5 h, 6 h, 7 h, 8 h, 10 h and 12 h. h from the beginning of the infusion. For the assessment of enzymatic activity, the following assessment times will be taken: pre-dose (0 h), 1 h, 3 h, 5 h, 5.5 h, 6 h, 7 h, 8 h, 10 h and 12 h. For the assessment of immunogenicity, the following evaluation times will be taken: pre-dose (0 h) and 12 h. • Visit III, IV, V and VI (telephone contact): The principal investigator or the delegated medical staff will contact the volunteer by telephone after Visit II to ask about medication tolerance and the presence of adverse events to the days 3, 7 and 14 respectively. • Visit VII (end of study visit): It will be carried out 35 days after Visit I, to evaluate the general clinical and biological status of volunteers. The same studies performed at the initial visit will be repeated. For the assessment of immunogenicity, samples will be taken to be evaluated at 35 days.
INVESTIGATIONAL PRODUCT/S DOSAGE AND ROUTE OF ADMINISTRATION	
A single dose of 1 mg/kg of agalsidase beta will be administered intravenously in an accurate strength to each volunteer for 5 h.
 
The following formulations will be used:
 
 • Sanofi Genzyme Fabrazyme® (Reference Formulation, "R") supplied as 35 mg and 5 mg lyophilized powder to be reconstituted for infusion. • Agalsidase beta, a biosimilar developed by Biosidus S.A. (Test Formulation, "T") supplied as 35 mg and 5 mg lyophilized powder to be reconstituted for infusion.
COMPARATIVE ASSESSMENT OF	From the results of the serum concentration of agalsidase beta, at the different sampling times, the following variables will be estimated:

PHARMACOKINETICS AND BIOLOGICAL ACTIVITY BETWEEN FORMULATIONS	
 - AUC_{0-12h}: area under the serum concentration curve between time 0 and 12 hours. - $AUC_{0-\infty}$: area under the serum concentration curve, as a result of the extrapolation between time 0 and infinite time. - C_{max}: maximum serum concentration of agalsidase beta. - T_{max}: time to maximum serum concentration for agalsidase beta. 
The difference between the T_{max} of the test formulation and that of the reference will be analyzed, and the drug elimination rate constant (Kel) and half-life ($t_{1/2}$) in the body will be calculated.
 
Summary measures (arithmetic and geometric means, standard deviation, CV% and range) for each formulation, as well as the individual results of each volunteer will be presented.

STATISTICAL ANALYSIS:	
SAMPLE SIZE CALCULATION:
 
The sample size ($n: 20$) was established based on data from the literature. As it is a sequential design, if the statistical analysis on the first 20 volunteers does not demonstrate bioequivalence, additional volunteers will be included for the eventual demonstration of bioequivalence with adequate power.

ANALYSIS PLAN	
COMPARATIVE PHARMACOKINETIC ANALYSIS BETWEEN FORMULATIONS
 
 - ABC_T / ABC_R: Ratio between the area under the curve for the Test formulation and the area under the curve for the Reference formulation. For log transformation, the 90% confidence interval of the AUC ratio (for AUC_{0-120h} and $AUC_{0-\infty}$) should be within the range of 0.80-1.25. - $C_{max\ T} / C_{max\ R}$: Ratio between the C_{max} of the Test formulation and C_{max} of the Reference formulation. For logarithmic transformation, the 90% confidence interval of the C_{max} ratio should initially be within the range of 0.80-1.25. 
COMPARATIVE ENZYME ACTIVITY ANALYSIS BETWEEN FORMULATIONS
 
 - Variation in the enzymatic activity for agalsidase beta in the sample at the end of infusion (5 h) compared to baseline (pre-infusion). For logarithmic transformation, the 90% confidence interval of the C_{max} ratio should initially be within the range of 0.80 -1.25. 
For an estimation of the pharmacokinetic parameters, specific pharmacokinetic computer softwares will be used (WinNonlin

Professional Edition, version 5.2.1 (2008).

Possible inter-subject and inter-treatment differences will be studied using ANOVA.

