4 STUDY DESIGN

Pharmacokinetics, biological activity and immunogenicity will be studied in 20 healthy volunteers starting with a single dose of 1 mg/kg/body weight after administration via intravenous infusion of one (1) dose of:

- Sanofi-Genzyme Fabrazyme®. (Reference Formulation, "R"), or
- Biosidus SA Agalsidase beta (Test Formulation, "T")

This study was conducted under an open, randomized, parallel-arm, balanced, and sequential design. As it is a sequential design, if the statistical analysis of the first 20 volunteers does not show bioequivalence, additional volunteers will be included until the similarity criterion is verified with adequate power.

For volunteers and clinical staff, the study is open. Laboratory determinations will be completed in a blinded fashion, with coded samples.

Below (Figure 1), a study visit scheme is presented:

[figure not shown]

Figure 1 Study Visit Scheme

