4.2 CODE UNBLINDING IN BLINDED STUDIES

This study is open to clinical staff, and is only blind for measurements to be made in the laboratory, which will be further carried out, when all the study samples are collected. Therefore, both the sponsor and the principal investigator will know the treatment received by each volunteer. The pharmacokinetic, enzyme activity and immunogenicity samples will be blind during dosing, and will be sent to the relevant laboratories presenting only the identification code of each subject.

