4.4.3 Analytical Method

Samples

All serum or plasma samples will be stored in duplicate at -20°C. Before the assay, the samples should be allowed to reach room temperature (15 °C - 28 °C) and mixed by gentle stirring. Aliquots from the samples will be made to prevent freezing - repeated thawing. The duplicate shall be kept at -20 °C.

Quantification Method

Pharmacokinetic Quantification:

Samples will be shipped at -20°C to Shin Nippon Biomedical Laboratories (SNBL), Ltd.

The agalsidase content will be quantified by the electrochemiluminescence method. The SNBL laboratory will validate the quantification method before the study is initiated.

Enzyme Activity Quantification

For the measurement of the biological enzyme activity in the plasma samples, the fluorimetric method of hydrolysis of the synthetic substrate 4-MU-Gal will be used.

Immunogenicity Measurement

Serum samples will be incubated with 1 ng beta agalsidase for 15 minutes at room temperature. Then, the sample enzymatic activity will be measured using the 4-MU-Gal substrate.

The inhibition percentage of the samples will be determined by comparing the activity value of 1 ng agalsidase beta with the treated samples. Those samples with percentage inhibition > 50% will be designated as positive.

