Annex 3: Storage and labeling

Each treatment unit corresponds to one bottle for intravenous administration of Biosidus Agalsidase or Sanofi Genzyme Fabrazyme® for a period of 5 hours.

Bottle label for each patient contains the following information: Protocol No: RD-BIO—AGA-01/03/21

Bottle N°:

Patient Initials: _____

Pacient N°: _____

Investigator's Name: [name]

Date of provision: _____

Lot N°:

Date of Expiration: November 30, 2021

Store between 2°C to 8°C, protect from heat, light and excessive moisture.

For exclusive use in clinical research. Keep out of reach of children.

Biosidus [name]

Note: Bottle N° 1 with 35 mg or Bottle N° 2 with 5 mg.

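### If the study extends beyond 20 volunteers, the planned ANOVA has no stage term, so a shift common to both arms between assay campaigns would widen the pooled 90% CI and, with unequal extension arms, bias the ratio

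*Combined protocol and SAP*

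**What the plan says.** The Protocol Summary (Analysis Plan) sets the criterion that the 90% CI for the log-scale T/R ratio of AUC and Cmax lies within 0.80-1.25. On the model it says only: "Possible inter-subject and inter-treatment differences will be studied using ANOVA". Section 7.1.1 repeats the criterion and names software. Section 10 gives the sample size. Neither states a model for combining stages, and no stage, cohort or assay-run term appears elsewhere.

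The extension depends on results. The Protocol Summary (Statistical Analysis) says "if the statistical analysis on the first 20 volunteers does not demonstrate bioequivalence, additional volunteers will be included", and section 4 says "additional volunteers will be included until the similarity criterion is verified with adequate power". No extension size or number of extensions is given.

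On assay timing, section 4.2 describes the study as "only blind for measurements to be made in the laboratory, which will be further carried out, when all the study samples are collected". Section 4.4.3 says "The agalsidase content will be quantified by the electrochemiluminescence method", at one external laboratory that validates the method before the study starts. Duplicate aliquots are kept, but re-assay of the first 20 alongside later samples is not planned.

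Section 4 calls the design balanced, and Annex 4 lists 10 R and 10 T for numbers 1-20. Section 4.6 numbers added volunteers from 21, for whom no allocation list is given.

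**The concern.** The decision to extend needs the concentrations of the first 20. Samples from number 21 onwards therefore cannot share their assay campaign. This is an inference, but a forced one: section 4.2 can stand beside the interim analysis only if all samples means those of the first 20.

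Levels may differ between campaigns in both arms alike. A treatment-only model treats that difference as between-subject noise. The interval is then wider than it need be, and more healthy volunteers might be dosed before it fits inside 0.80-1.25. If the extension arms are unequal, part of the shift also enters the T/R ratio. This is separate from the error rate of repeated testing.

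**Working it through.** **The plan's own figure.** Inputs from section 10: ratio 1.0, CV 0.15, power 0.80, α = 0.05 per one-sided test, limits 0.80-1.25. The log-scale variance is σ² = ln(1 + 0.15²) = 0.02225, so σ = 0.1492. Exact power for two one-sided t-tests is 0.769 with 8 per group, 0.836 with 9 and 0.884 with 10. The stated 9 per group reproduces, and 9 + 1 per group gives 20.

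**Assumed inputs.** The documents give neither a between-stage shift nor an extension size. I take one extension of 20 volunteers and a multiplicative shift common to both arms of 5% to 30%. Write d = ln(1 + shift).

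**Balanced extension (10:10).** Without a stage term, each arm of 20 has half its values moved by d. The expected residual variance becomes σ² + (d²/4)(40/38). The relative CI width is the square root of the variance ratio. The volunteers effectively lost are 40 × (1 − 1/variance ratio).

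| Shift | d | Variance ratio | CI width | Volunteers lost, of 40 |
|---|---|---|---|---|
| 5% | 0.0488 | 1.028 | +1% | 1 |
| 10% | 0.0953 | 1.107 | +5% | 4 |
| 20% | 0.1823 | 1.393 | +18% | 11 |
| 30% | 0.2624 | 1.814 | +35% | 18 |

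Simulation agrees. The mean log half-width with a stage term is 0.079 at every shift. Without it, the half-width is 0.080, 0.083, 0.093 and 0.107 in turn. With no shift both models give 0.079, so the term costs nothing measurable. The ratio is unbiased in both models. One-sided type I error without the term falls from 0.05 to about 0.04 at a 10% shift and 0.025 at 20%, so the omission is conservative here.

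**Unequal extension.** With a Test and b Reference volunteers added to 10 + 10, the log-scale bias without a stage term is d × [a/(10+a) − b/(10+b)].

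- 12:8: 12/22 − 8/18 = 0.101. Bias +1.0% at a 10% shift and +1.9% at 20%. Simulated type I error at the nearer limit is about 0.06.
- 10:9 (one loss): 10/20 − 9/19 = 0.026. Bias about 0.3% and 0.5%.
- 7:3 (a smaller extension): 7/17 − 3/13 = 0.181. Bias +1.7% and +3.4%. Type I error about 0.08 and 0.09-0.10.

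With the stage term, bias is nil and type I error is 0.05 in the 12:8 and 7:3 simulations.

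**Limits.** The type I error rates do not condition on failure in the first 20 and do not address repeated looks.

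**The case against.** The strongest objection is that the size of the problem is assumed. The only related figures are the Reference lot readings in Annex 7. These run from 5.3 to 5.4 mg/mL, a spread of 1.9% (5.4/5.3), seen only among 5 mg vials. At a 2% common shift the CI is 0.2% wider. At the plan's own inputs the first 20 fail only about 12% of the time (1 − 0.884). Given that failure, the pooled 20 + 20 analysis passes with probability about 0.98 with or without the term at a 10% shift, and 0.95 against 0.98 at 20%. The gap becomes material when a less favourable ratio meets a large shift: at an assumed true ratio of 0.93 and a 20% shift, about 0.70 against 0.81. All of this stands and limits the size of the point.

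The documents also do not expressly tie the CI to this ANOVA or say that stages are pooled, and a subject term cannot be estimated in a single-dose parallel design. That also stands, but no other model is named.

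Three stronger readings are tempting and not supported:

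- **Bias is expected.** It needs unequal extension arms. The design is described as balanced, and a list ending at 20 is not a plan for 12:8.
- **New lots make a stage term necessary.** The label reads "Date of Expiration: November 30, 2021", so a reader might infer that extension volunteers would receive other lots. No lot or dosing schedule is given, and section 6.1.2 requires comparative activity testing of all batches to be used. A new lot of one product shifts one arm only, which a stage main effect does not remove.
- **Enzyme activity is affected in the same way.** Section 7.2 compares activity at 5 h with the volunteer's own baseline. If that is analysed as a ratio, a multiplicative assay shift largely cancels.

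**Conclusion.** The point holds as a cheap improvement to the analysis of AUC and Cmax, conditional on an extension with pooled stages. The named model omits a factor that the sequential design creates. For 20 + 20 at CV 0.15, the cost is a CI about 1%, 5% or 18% wider at assumed common shifts of 5%, 10% or 20%.

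A reader might infer that the omission generally favours a false finding of similarity. With balanced extension arms it does the opposite. Type I error rises only at one limit and only when the extension arms are unequal; the corresponding bias in the ratio is about 1% to 2% for 12:8 and 0.3% to 0.5% for a single loss, at 10% to 20% shifts.

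**What to change.** State in the Protocol Summary and section 7.1.1 that, if the study is extended and stages are pooled, the 90% CIs come from an ANOVA on the log scale with fixed effects for treatment and stage. Give stage one level for the first 20 and one for each later extension or assay campaign. A single level for everyone from 21 onwards would merge the several extensions that section 4 allows. State also that each extension is randomised 1:1 within its stage.

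Reconcile section 4.2, which has the laboratory measure "which will be further carried out, when all the study samples are collected", with the analysis of the first 20 described in the Protocol Summary and section 4.

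The cost is a few sentences and one residual degree of freedom per added stage, with no extra volunteers or samples. Settling the model in advance also avoids choosing it after the first 20 results are known in a study that section 4.2 leaves open to the sponsor and investigator.
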